4.2.2 Guidance on concomitant treatments

There are no restrictions on concomitant treatment. All concomitant treatments as prescribed by the patient's healthcare professionals are allowed. Patients will continue to take all medicines as prescribed by their healthcare professionals.

There are no restrictions on diet or life-style. Patients will continue to follow all instructions on diet, exercise and lifestyle as directed by their healthcare professionals.

4.3 Treatment compliance

Patients will use the patientMpower app to record daily compliance with medications prescribed for treatment of their IPF (if they are receiving medications for treatment of IPF).

5 Variables and their assessment

5.1 Efficacy

The objectives of this observational study are:

- to assess and characterise the longitudinal trends of patient-measured FVC and PROMs in a cohort of patients with IPF
- to determine the correlation (if any) between patient-measured FVC and PROMs with clinic-observed measurements
- to assess if longitudinal trends in patient-measured FVC outcomes are predictive of clinical health outcomes in IPF
- to assess the acceptability and utility of the patientMpower app

5.1.1 Efficacy endpoints

5.1.1.1 Primary endpoint

The primary endpoint is the longitudinal trend in patient-reported FVC. The correlation between patient-reported FVC and clinic-reported measures and outcomes will also be assessed.

The primary endpoint variable is the daily patient-reported FVC.

5.1.1.2 Secondary endpoints

The secondary endpoints include

- the longitudinal trend in PROMs
- the correlation between patient-reported measures (PROMs) and clinic-reported measures and outcomes.
- assessment if patient-measured FVC predicts clinical health outcomes
- the impact of active engagement and self-monitoring using the patientMpower app on the impact of IPF on daily life (PROM)
- the effect of the patientMpower app on medication compliance
- the acceptability and utility of the patientMpower app (from patient and healthcare professional perspective)

The secondary endpoint variables (reported by patients) are:

- maximum level of dyspnoea each day (ideally linked to description of activity causing maximum dyspnoea)
- activity (number of steps/day)
- distance walked per day
- compliance with medicines prescribed for treatment of IPF
- addition of any new prescribed medicines for treatment of IPF
- impact of their medical condition on their daily life (once/week; responses to questions in PROM)

Additional secondary endpoint variables which can be recorded by the patients (if measurement devices are available to the patient and it is practical for the patients to record these variables) include:

- duration of walking per day
- number of episodes of walking per day
- cough (worst severity each day)
- heart rate (if patient has access to wearable fitness device)
- blood pressure (if patient has access to measurement device)
- temperature (if patient has access to measurement device)
- body weight (once/week)
- oxygen saturation at rest (if patient has access to pulse oximetry device and wishes to record saturation)
- oxygen consumption (cylinders/month)

Patients will assess dyspnoea with the mMRC dyspnoea scale [12] which may be a useful prognostic indicator in IPF [13].

The secondary endpoint variables (assessed and recorded by the clinic) are:

- FVC
- Dyspnoea [e.g. University of California San Diego (UCSD) Shortness of Breath Questionnaire or other measure usually used by the research sites] [14]
- impact of the patient's medical condition on their daily life (using the same PROM questions used by the patient)
- health outcomes e.g.
 - medication adherence
 - change in IPF medication (dose change or new medicine prescribed)
 - o oxygen usage
 - o exacerbations of IPF
 - o hospitalisations due to IPF

The patient's opinion of the utility and acceptability of the patientMpower app as assessed by their response to questions:

- the instructions given in using the patientMpower app were clearly understandable (strongly agree/agree/disagree/strongly disagree)
- using the patientMpower app helped me to take the correct dose of my medicines for lung fibrosis every day (strongly agree/agree/disagree/strongly disagree) [only asked if patient is taking medication specifically prescribed for IPF]
- using the patientMpower app helped me to reach my personal exercise goal every day (strongly agree/agree/disagree/strongly disagree)
- using the patientMpower app helped me to walk further (or exercise more) compared with before (strongly agree/agree/disagree/strongly disagree)
- using the patientMpower app gave me more confidence/a greater sense of control in managing my lung health (strongly agree/agree/disagree/strongly disagree)
- I found it useful to be able to record the impact of lung fibrosis on my daily life (strongly agree/agree/disagree/strongly disagree)
- I liked using the patientMpower app (strongly agree/agree/disagree/strongly disagree)
- the patientMpower app was easy to use (strongly agree/agree/disagree/strongly disagree)
- the effect of using the patientMpower app on the impact of lung fibrosis on my well-being and daily life (positive, negative)
- I found it tiring or irritating to use the patientMpower app (strongly agree/agree/disagree/strongly disagree)

- I want to continue using the patientMpower app after the end of the study (yes, no)
- I would recommend other people with my condition to use the patientMpower app (yes/no)
- what other measurements, reminders or information would be useful to have on the patientMpower app? (Open text for participant to give opinion)
- describe the benefits and/or disadvantages of using the patientMpower app (Open text for participant to give opinion)

The secondary endpoint will also be assessed by the healthcare professional's response to the following questions:

- preference for using the patientMpower app versus not using it (yes, no preference, no)
- difficulty rating in using the patientMpower app (very easy, easy, difficult, very difficult)
- did using the patientMpower app help me to help the patient manage their IPF better? (yes, no)
- did using the patientMpower app help the patient to take their IPF medicines at the correct dose every day (yes, no) [only asked if patient is taking medication specifically prescribed for IPF]
- do I believe the patient should continue using the patientMpower app after the end of the study (yes, no)
- what other measurements, reminders or information would be useful to have on the patientMpower app? (Open text for healthcare professional to give opinion)
- describe the benefits and/or disadvantages of using the patientMpower app (Open text for healthcare professional to give opinion)

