Installation of		Х		
patientMpower app & pair				
spirometer				
Record compliance or	Х		Х	X ³
changes (IPF medicine) ²				
Patient-measured FVC ²	Х		Х	Х
Record impact of IPF (PROM) ^{4,5}	X4		X ⁵	X ⁴
Patient outcomes (e.g.			Х	
oxygen consumption,				
dyspnoea, pulse oximetry,				
symptoms, vital signs) ⁶				
Utility & acceptability of				Х
app ⁷				
Clinic-reported outcomes				Х
(e.g. exacerbations)				
End of study				Х

¹ End of study visit will be date of usual scheduled clinic visit.

² Reported by patient on patientMpower app every day. Goal is for patient to record one FVC measurement (seated) per day.

³ Clinic to record changes in IPF medication or other medicines prescribed for respiratory conditions.

⁴ Impact of IPF on daily life (Patient Reported Outcome Measure; PROM) to be assessed by clinic team at baseline and end of study visit and recorded on patientMpower app.

⁵ Impact of IPF on daily life (PROM) to be reported by patient on patientMpower app every week.

⁶ Reported by patient as often as possible, ideally each day. These measurements are optional and will only be recorded where practical for the patient.

[figure not shown]
⁷ Patient and healthcare professional perspective. If patient is withdrawn prematurely, try to capture patient perspective of utility and acceptability of app at time of withdrawal.

List of Tables

None

List of Figures

Figure 1: Patient recruitment process

List of Abbreviations

AE Adverse event ATS American Thoracic Society BI Boehringer Ingelheim	
·····	
Pl Deshringer Ingelheim	
BI Boehringer Ingelheim	
DLCO Diffusing Capacity of the Lung for Carbon Monoxide	
ERS European Respiratory Society	
FEV ₁ Forced Expiratory Volume in 1 second	
FVC Forced Vital Capacity	
IEC Independent ethics committee	
ILFA Irish Lung Fibrosis Association	
IP Internet Protocol	
IPF Idiopathic pulmonary fibrosis	
IRB Institutional review board	
JRS Japanese Respiratory Society	
K-BILD King's Brief Interstitial Lung Disease Questionnaire	
MIR Medical International Research	
mMRC modified Medical Research Council	
PEF Peak Expiratory Flow	
PFW PF Warriors of Texas	
PROMpatient reported outcome measure	
SSH Secure Shell	
SSL Secure Sockets Layer	
TLS Transport Layer Security	
UCSD University of California San Diego	

1. Introduction

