3.2 Discussion of study design

This is an open-label, single group observational study. There is no control group.

Patients will follow their usual care programme throughout the study. The study observation period (16 ± 8 weeks) is approximately equal to the interval between clinic visits in the usual care of IPF.

This design will enable assessment of longitudinal trends in FVC and PROMs in a cohort of patients with IPF undergoing usual care.

Patients enrolled in the study will capture information on relevant health outcomes related to IPF on a regular basis (daily for some parameters) using the patientMpower app. Patients will also measure FVC at home once per day using the Spirobank Smart spirometer. The patient measured FVC and other spirometry data will be captured automatically by the patientMpower app. These data will form the patient-reported outcome database.

Clinical assessments (e.g. FVC, dyspnoea) in the same cohort of patients will be assessed at the beginning and end of the study. PROMs will also be recorded at the clinic at the beginning and end of the study. This design allows comparison of patient-reported data and their longitudinal trends with clinic-reported data in a cohort of patients with IPF. The correlation between the two types of data and the value of patient measurements in predicting health outcomes can be assessed and quantified.

This design will also allow evaluation of the utility and acceptability of the patientMpower app in a patient population managed by centres with expertise in the diagnosis and management of IPF. This will be assessed from both the patient and healthcare professional perspectives.

The patientMpower app will include key questions derived from a PROM developed specifically for patients with IPF [5] and will help to evaluate the utility of an electronic health diary in capturing PROM data in IPF patients.

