6.2.2 Baseline clinic visit

The study procedures and assessments during the observation period at each clinic visit are summarized in flow-chart 2 on page 7.

At a usual care visit to the study centre, the research team will discuss the study with the patient (face-to-face), confirm their understanding of the study processes and their willingness to participate.

Written informed consent will be obtained before any study-specific assessments and before installation of the patientMpower app.

The study starts at this visit.

The patient will be instructed in the correct use of the Spirobank Smart home spirometer and uploading of data to the patientMpower app. The patient's understanding of the patientMpower app, Spirobank Smart home spirometer and the study procedures should be checked before they leave the clinic.

Demographic data, medical history and concomitant therapy for IPF and other respiratory conditions will be recorded.

The following parameters will be assessed and recorded in the clinic records:

- spirometry (to include FVC)
- dyspnoea (e.g. UCSD Shortness of Breath Questionnaire or other measure usually used by the investigator sites) impact of IPF on daily life (using the same PROM as in the patientMpower app)

The study centre will advise patientMpower Ltd that the patient has consented to participate in the study and provide the patient's contact details.

patientMpower Ltd. will send the patient an information pack (via email) and a home spirometer (via regular mail or courier). The information pack will give instructions (including video clips) on how to install the patientMpower app onto your smartphone or tablet device and how to pair the spirometer with the app. During the installation, some information on the patient (e.g. date of birth and gender) will be recorded on the patientMpower app. If necessary, the patient may be loaned a tablet device (like an iPad) which will have the patientMpower app installed. If requested by the patient, patientMpower Ltd. will provide technical support to the patient in downloading the app and pairing with the spirometer.

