6.2.4 End of treatment clinic visit (16 \pm 8 weeks) and follow-up period

The following parameters will be assessed and recorded in the clinic records:

- spirometry (to include FVC)
- dyspnoea (e.g. UCSD Shortness of Breath Questionnaire or other measure usually used by the investigator sites)
- impact of IPF on daily life (using the same PROM as in the patientMpower app)
- medication adherence (if prescribed for IPF)
- changes in or addition of any new medicines for the treatment of IPF (if prescribed)
- exacerbations of IPF since previous visit
- hospitalisations due to IPF since previous visit

The patient and healthcare professional opinion on the usefulness and acceptability of the patientMpower app will be assessed and recorded. (The questions are described in section 5.1.1.2 above.)

7. Statistical methods and determination of sample size

This a pilot study to assess the feasibility of patients with IPF using the patientMpower app including home-based FVC to monitor their health.

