7.6 Determination of sample size

This is pilot study. The proposed sample size of 25 subjects has been chosen arbitrarily.

8. Informed consent, data protection and study records

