1.1 Protocol

The study protocol was finalised on 11 January 2018 [1].

This was an open-label, single-group observational study of a population of idiopathic pulmonary fibrosis (IPF) patients treated with usual care. There was no control group.

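### Two secondary endpoints are worded as effects of the app, but the single-arm design cannot attribute any change to it; for compliance, even a before-after change is doubtful

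*Protocol*

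**What the plan says.** Among the secondary endpoints in Protocol 5.1.1.2 are "the effect of the patientMpower app on medication compliance" and "the impact of active engagement and self-monitoring using the patientMpower app on the impact of IPF on daily life (PROM" (closing bracket omitted). SAP 4.1 repeats both. On design, Protocol 3.2 says "There is no control group" and SAP 1.1 says "There was no control group". Neither document states a hypothesis, and Protocol 7.6 says "The proposed sample size of 25 subjects has been chosen arbitrarily".

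The compliance data are described in four places in the protocol:

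- **Baseline visit (6.2.2).** The list opening "The following parameters will be assessed and recorded in the clinic records" covers spirometry, dyspnoea and the PROM. Concomitant IPF therapy is also recorded. Adherence is not listed.
- **End visit (6.2.4).** The list includes "medication adherence (if prescribed for IPF" (closing bracket omitted), together with the PROM.
- **Flow chart 2.** The compliance row is marked at baseline, daily and at the end. The row carries footnote 2: "Reported by patient on patientMpower app every day".
- **Section 4.3.** Patients receiving IPF medicines record daily compliance with them on the app.

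Missing data are not imputed (Protocol 7.4, SAP 5.3). Questionnaires ask patients and healthcare professionals whether the app helped with taking the correct dose. Patients also rate the app's effect on their well-being and daily life.

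**The concern.** An effect or impact of the app is a contrast between using it and not using it, and the study observes only patients who were given it. SAP 5.3 describes changes over time and correlations, and offers no method for an app effect.

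Compliance has two further problems. A paired value from before the app may not exist, and the daily record is made through the intervention itself, so it covers only days with an entry. A high recorded figure could then be read as evidence that the app works, when it may reflect the patients' prior habits, the days they chose to record, or both.

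The engagement-PROM endpoint could be examined by comparing heavier with lighter users. Health status may influence how often a patient records, however, and SAP 5.3 describes no adjustment for this.

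**Working it through.** There is no planned figure to reproduce: the documents give no alpha, power, effect size or SD, and the sample size of 25 is stated to be arbitrary. The check is mainly about what the design can identify.

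**Step 1. Which measurements exist for each endpoint**

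| | Before the app | During app use | End visit | Comparator without app |
|---|---|---|---|---|
| PROM | Clinic, 6.2.2 | Weekly, app | Clinic, 6.2.4 | None |
| Compliance | Unclear: absent from 6.2.2, marked in flow chart 2 | Daily, app | Clinic, 6.2.4 | None |

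The last column is empty for both endpoints, so neither supports an attributable effect. The PROM row supports a paired change.

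**Step 2. The baseline compliance mark**

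Section 6.2.2 points to flow chart 2 as the summary of visit procedures, so the mark cannot be ignored. But footnote 2 makes the app the source, and the chart places installation at day 0-2. Under section 6.2.1 the instructions and spirometer are sent within two working days of the baseline visit. The same footnote and a baseline mark also apply to patient-measured FVC, so the mark does not by itself show clinic capture. The documents do not settle whether a pre-app adherence value was taken.

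**Step 3. How far app-recorded compliance pins down true compliance**

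Let u be the share of days on medication with an entry and c the compliance on those days. If unrecorded days are treated as unknown:

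- lower bound = u × c
- upper bound = u × c + (1 − u)

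The documents give neither u nor c. Assuming c = 0.98:

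| u | Lower | Upper |
|---|---|---|
| 0.9 | 0.9 × 0.98 = 0.882 | 0.882 + 0.1 = 0.982 |
| 0.7 | 0.7 × 0.98 = 0.686 | 0.686 + 0.3 = 0.986 |
| 0.5 | 0.5 × 0.98 = 0.490 | 0.490 + 0.5 = 0.990 |

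The width is always 1 − u, so it depends only on recording frequency. These bounds describe the level of compliance while the app is in use. They do not measure an app effect.

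**Step 4. Precision of an uncontrolled paired change**

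The 95% half-width, in SDs of the change, is t(0.975, n−1)/√n:

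- n = 25 (planned): 2.064/5.000 = 0.41
- n = 20 (treated dataset): 2.093/4.472 = 0.47
- n = 18: 2.110/4.243 = 0.50

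The last case assumes that both patients without an end visit (SAP 1.3) belong to the treated dataset. More patients would narrow these intervals but would not supply a comparator.

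**The case against.** The strongest reply is that this is a descriptive pilot with no hypotheses, that SAP 5.3 plans no effect estimate, and that nothing in the documents says an effect will be claimed. That stands in part. It makes this a matter of endpoint wording and reporting, and it would be unfair to presume that the results will be misreported. It does not justify naming an effect as an endpoint in both documents.

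Three stronger readings are tempting, and the documents do not support them:

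- **Nothing can be estimated for either endpoint.** The PROM is taken in clinic at both visits with the same questions, so a before-after change is available. What is missing is attribution.
- **No treated patient has a pre-app adherence value.** This takes one side of the conflict between section 6.2.2 and flow chart 2. Protocol 5.1.1.2 also lists adherence as a clinic-assessed variable without tying it to one visit, and day 0-2 includes the visit day. The relevant group would in any case be patients on IPF medication, whose number is not given, and not all 20 treated patients.
- **App entries are the only compliance information.** The clinic records adherence at the end visit, and perceived help with dosing is collected by questionnaire. The first lacks a listed baseline counterpart and the second is opinion, but both can be reported.

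The bounds also assume that a missed day is never filled in later, which the documents do not address. SAP Appendix 1, which holds the list of comparisons and tests, was not available. It might specify an analysis, but no analysis could create the missing comparator.

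**Conclusion.** The point holds in this form. The endpoint wording goes further than a single-arm design allows: no effect attributable to the app can be estimated for compliance or for the PROM. That conclusion needs no numerical assumption.

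For the PROM, the supportable result is an uncontrolled change from baseline, with a 95% half-width of about 0.47 SD of the change at n = 20. For compliance, a paired change is in doubt until the baseline passages are reconciled. The app-recorded level can be loosely determined: 69% to 99% with 70% of days recorded, and 49% to 99% with 50%. Both ranges rest on the assumed 98% compliance on recorded days, on assumed recording shares, and on no later entry of missed days. They should not be read as evidence that compliance was low or that recorded figures are too high.

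**What to change.** 1. **Wording.** In Protocol 5.1.1.2 and SAP 4.1, restate the endpoints as change in PROM from baseline during app use, recorded compliance during app use, and perceived helpfulness. State that no effect is attributed to the app.
2. **Reporting.** Among patients on IPF medication, report app-recorded compliance with all days on medication as the denominator, the share of days recorded, and bounds that treat unrecorded days as unknown. Show the clinic end-visit adherence alongside.
3. **Baseline item.** Reconcile flow chart 2 with section 6.2.2 and state whether, and how, adherence was recorded before installation. In any future version of the protocol, list the same clinic adherence item at baseline as at the end visit. This would give a paired change, still not an app effect.

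Items 1 and 2 can be done at reporting, at the cost of some text and a few table columns. The new baseline item in 3 adds one question to a visit already held. It cannot help the present patients, because SAP 2.3 closes follow-up of the last two on 30 April 2020. The main downside is a weaker claim for the app.

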- impact of the patient's medical condition on their daily life (using the same PROM questions used by the patient)
- health outcomes e.g.

- medication adherence
- change in IPF medication (dose change or new medicine prescribed)
- oxygen usage
- exacerbations of IPF
- hospitalisations due to IPF

The patient's opinion of the utility and acceptability of pMp as assessed by their response to questions:

- the instructions given in using pMp were clearly understandable (strongly agree/agree/disagree/strongly disagree)
- using pMp helped me to take the correct dose of my medicines for lung fibrosis every day (strongly agree/agree/disagree/strongly disagree) [only asked if patient is taking medication specifically prescribed for IPF]
- using pMp helped me to reach my personal exercise goal every day (strongly agree/agree/disagree/strongly disagree)
- using pMp helped me to walk further (or exercise more) compared with before (strongly agree/agree/disagree/strongly disagree)
- using pMp gave me more confidence/a greater sense of control in managing my lung health (strongly agree/agree/disagree/strongly disagree)
- I found it useful to be able to record the impact of lung fibrosis on my daily life (strongly agree/agree/disagree/strongly disagree)
- I liked using pMp (strongly agree/agree/disagree/strongly disagree)
- pMp was easy to use (strongly agree/agree/disagree/strongly disagree)
- the effect of using pMp on the impact of lung fibrosis on my well-being and daily life (positive, negative)
- I found it tiring or irritating to use pMp (strongly agree/agree/disagree/strongly disagree)
- I want to continue using pMp after the end of the study (yes, no)
- I would recommend other people with my condition to use pMp (yes/no)
- what other measurements, reminders or information would be useful to have on pMp? (Open text for participant to give opinion)
- describe the benefits and/or disadvantages of using pMp (Open text for participant to give opinion)

The secondary endpoint will also be assessed by the healthcare professional's response to the following questions:

- preference for using pMp versus not using it (yes, no preference, no)
- difficulty rating in using pMp (very easy, easy, difficult, very difficult)
- did using pMp help me to help the patient manage their IPF better? (yes, no)

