5.3 Planned analysis

All data from the Treated data set were included in the analysis. The list of variables, data formats, data presentations, statistical comparisons and statistical tests used are shown in Appendix 1 (section 7).

Results were summarised for descriptive statistical display. No imputations of missing data were made.

The primary efficacy endpoints were assessed by analysis of changes in patientreported FVC, clinic-derived parameters and health outcomes over time.

Patient-reported FVC and other patient-reported measures were compared with the clinic-derived measures and health outcomes to determine if there were any correlations between them.

The secondary endpoints data were assessed by analysis of changes in the patient-reported health parameters, clinic-derived parameters and health outcomes over time.

Data on the level of engagement with pMp and the patient opinions were described and tabulated.

Patient-recorded FVC data were screened to detect outlier values (e.g. where a patient did not blow forcefully enough or may have coughed during the forced expiratory maneuver). The average patient-recorded FVC was tracked over time via the Exponentially Weighted Moving Average (EWMA) adjusted for irregular time indices [5,6]. Control limits were constructed via the EWMA variance, which accounted for the stochasticity around the mean, plus an adjustment 0.15*log(max(delta_t, 1)), where delta_t is the time since the last observation, for the purpose of modelling our uncertainty due to lack of engagement during periods where the patient was not inputting spirometry values. Any values outside these control limits were considered outliers. Scatter plots of patient-recorded FVC versus time were prepared for each patient.

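### The patient item on the app's effect on well-being and daily life has no 'no effect' option, so its positive share is at best an upper bound on the share who perceived a benefit

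*Protocol*

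**What the plan says.** The patient opinion questionnaire is listed in protocol 5.1.1.2 and repeated in SAP 4.1. It has 14 questions, of which 12 are closed. The item at issue appears in the protocol as "the effect of using the patientMpower app on the impact of lung fibrosis on my well-being and daily life (positive, negative" and in the SAP as "the effect of using pMp on the impact of lung fibrosis on my well-being and daily life (positive, negative". Both documents print two options and no third. Neither tells a patient who noticed no effect what to do.

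Other closed items are built differently. Nine use a four-point agreement scale, for example "using the patientMpower app helped me to walk further (or exercise more) compared with before (strongly agree/agree/disagree/strongly disagree". Two more patient items are yes/no. The healthcare professional form has a three-way item, "preference for using the patientMpower app versus not using it (yes, no preference, no".

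The questionnaire serves the secondary endpoint "the acceptability and utility of the patientMpower app (from patient and healthcare professional perspective". On analysis, SAP 5.3 says "Data on the level of engagement with pMp and the patient opinions were described and tabulated" and "No imputations of missing data were made". It gives no denominator for the opinion items and no rule for a blank answer.

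**The concern.** Leaving the midpoint out of an agreement scale is a matter of preference, because a patient who gained nothing can still truthfully disagree. This item is of another kind. It asks for the direction of an effect and omits the case where there is none, which is a plausible experience of keeping an electronic diary for about 16 weeks. Such a patient has no truthful closed answer.

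What is at stake is how one line of the results table is read. A high positive percentage would naturally be taken as the proportion of patients whose daily life the app improved. Part of that percentage may consist of patients who noticed nothing and had to pick a side, or may come from a denominator that has lost them. No other item in the plan measures how many such patients there were.

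**Working it through.** The plan states no figure for this item. The sample size of 25 is described as arbitrary (protocol 7.6, SAP 5.5) and there are no hypotheses, so there is nothing to reproduce. The check has two parts.

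**1. Can each closed patient item express no effect?**

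- Nine agreement items: yes. Disagreeing with a statement that the app helped is truthful for a patient it did not help.
- Two yes/no items (continuing to use the app, recommending it): yes, because they ask about intention and not about an effect.
- The well-being item: no. Neither option is true for a patient with no effect.

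The open-text question, "describe the benefits and/or disadvantages of using the patientMpower app (Open text for participant to give opinion", lets a patient say so in words. Nothing links that text to the coding of the closed item.

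**2. How far can the reported share move?**

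Input from the documents: n = 20, the treated dataset in the SAP synopsis. Assumed, because the documents do not give them: the true numbers with a positive effect (P), no effect (Z) and a negative effect (N), with P + Z + N = n. Patients with a real effect are taken to answer truthfully.

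- All answer: the reported positive share lies between P/n (every no-effect patient chooses negative) and (P + Z)/n (every one chooses positive).
- All no-effect patients skip and blanks are dropped: the reported share is P/(P + N).

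| Assumed P / Z / N | True share | Reported, all answer | Reported, no-effect patients skip and are dropped |
|---|---|---|---|
| 10 / 8 / 2 | 10/20 = 50% | 10/20 to 18/20 = 50% to 90% | 10/12 = 83% |
| 6 / 12 / 2 | 6/20 = 30% | 6/20 to 18/20 = 30% to 90% | 6/8 = 75% |
| 16 / 2 / 2 | 16/20 = 80% | 16/20 to 18/20 = 80% to 90% | 16/18 = 89% |

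The width of the range is Z/n, the share of patients with no effect, which the form cannot record. Read backwards, a reported 18/20 = 90% with full response fits any true share from 0% (P/Z/N = 0/18/2) to 90% (18/0/2).

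**When the upper bound holds.** With full response the reported share is never below P/n. It also stays at or above P/n if only no-effect patients skip, as in the last column. The guarantee goes once blanks may come from anyone. Take 10/8/2 again, let 4 of the 10 positive patients leave the item blank, and let the 8 no-effect patients choose negative. The form then shows 6 positive, 10 negative and 4 blank. With blanks dropped, 6/16 = 37.5%, below the true 50%. Counting the blanks as possible positives restores a valid ceiling: (6 + 4)/20 = 50%. That is why the blank count over all patients asked has to be reported.

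**The case against.** The strongest case is that little depends on this item. It is one of 14 patient questions in a single-arm pilot with no hypotheses, and no threshold or decision uses it. Neighbouring items on confidence, walking further and the usefulness of recording impact let a patient report no benefit, and open text is available. This stands as a limit on the importance of the point. None of those items asks the same question, so they do not supply the missing answer.

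A reader might infer that the secondary endpoint on the app's effect on daily life rests on this item. The documents do not support that. Protocol 5.1.1.2 and SAP 4.1 name the PROM as the measure for that endpoint and place this item under utility and acceptability. The synopses do list the app's impact on self-management and daily living without naming an instrument, so some link is possible, but the body text does not make it.

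A reader might also infer that no-effect patients would lean towards *positive*. Nothing in the documents shows which way they would go. The 90% end of the ranges needs every one of them to choose *positive*.

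Two further cautions stand. SAP Appendix 1, which is said to hold the data formats, is not part of the text available, so the form as fielded could differ. Twenty respondents may also be optimistic. The questionnaire is scheduled for the end-of-study clinic visit, which two patients did not have (SAP 1.3), and the documents do not say whether they were asked in another way.

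**Conclusion.** The point holds, at minor weight. As printed in both documents, the item gives no truthful closed answer to a patient who noticed no effect. With full and truthful response, its positive share is an upper bound on the share who perceived a benefit. If blanks leave the denominator, that bound holds only on an assumption about who left them.

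To go further and call the result uninterpretable would be too strong, because an upper bound is still information and is a tight one when few patients are neutral (80% to 90% in the 16/2/2 case). The size in this trial is unknown. All the ranges rest on assumed splits of 20 patients and on truthful answers from those with a real effect. The primary FVC endpoint and the PROM endpoints are not affected.

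**What to change.** - **Form:** in the questionnaire in protocol 5.1.1.2, and in any further use of it, offer *positive*, *no effect* and *negative*, and tabulate all three with the number not answering.
- **Data already collected:** the SAP is written after the fact, with follow-up of the last two patients cut off at 30 April 2020. The options in SAP 4.1 should therefore not be rewritten, since that would misdescribe the instrument. Add to SAP 5.3 that this item is reported as positive, negative and not-answered counts over all patients asked, is labelled as forced choice, and is read alongside the open-text answers. The positive share should not be presented as the proportion who benefited.

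The cost is one response option in future use, and one table row with a footnote now. The downside is a possibly lower reported positive percentage.
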